6.6.2.1.2 Saint George's Respiratory Questionnaire

As the SGRQ manual ([13](#)) allows for 25% of missing data per component (i.e., 2 questions for symptoms, 6 questions for impacts and 4 questions for activities) the rules defined in the SGRQ manual will be used to derive the SGRQ.

Additionally the responses to questions 5 and 6 will be made consistent to the extent that if the answer to question 5 is 5 (none of the time) and the answer to question 6 is non-missing (i.e., length of worst attack specified), then question 6 will be set to missing. Therefore scores will be calculated ignoring that item. In this case, the missing response to question 6 will not be included in the count of missing questions for the symptoms component.

If the patient did not receive any respiratory treatment, then Part 2 Section 5 of the SGRQ should be skipped to go directly to Section 6. In this case, based on SGRQ manual instructions, responses will be considered as zero (and thus will not be included in the count of missing questions for the impact component).

Missing questions from Part1 Section 1 ("If you ever held a job...") will be left as missing (and counted as missing).

6.6.2.1.3 Digital ulcer net burden

If the presence of a digital ulcer is missing for a finger, digital ulcer net burden will be set to missing.

6.6.2.1.4 HAQ-DI

According to HAQ-DI scaling and scoring manual, if there are fewer than 6 categories with responses, an index score cannot be calculated and will be set to missing (no imputation planned).

6.6.2.1.5 FACIT dyspnoea or functional limitations score

If there are missing items, subscale scores can be calculated by multiplying the sum of the subscale by the number of items in the subscale, then dividing by the number of items actually answered. However this is only acceptable if more than 50% of the items were answered (FACIT Administration and Scoring Guidelines). No imputation planned in case of missing score.

6.6.2.1.6 EQ-5D-5L (EuroQol 5-Dimensionnal quality of life questionnaire)

No imputation planned. No score will be derived.

6.6.2.1.7 CRISS

Index score calculation:

For patients who are considered as improved over 52 weeks, in case the absolute change from baseline to week 52 in mRSS, FVC %predicted, patient global assessment, physician global assessment or HAQ-DI score is missing, then CRISS index score will be considered as missing.

In the multiple imputations step, after transformation into a binary responder variable, missing values will be imputed using the worst case (i.e. as Non-responder in all the imputations).

6.6.2.1.8 Disease progression

The handling of missing data is summarised in the table below:

Table 6.6.2.1.8: 1 Handling of missing data for disease progression

Absolute change from baseline in FVC %predicted at 52 weeks	Change from baseline in mRSS (absolute and relative) at 52 weeks	Death	Disease progression	Missing data rule
Missing	Missing or no mRSS worsening	Alive	Yes	Worst case
Missing or no FVC worsening	Missing	Alive	Yes	Worst case
Missing or FVC worsening or no FVC worsening	Missing or mRSS worsening or no mRSS worsening	Death	Yes	None
Missing or FVC worsening or no FVC worsening	mRSS worsening	Alive	Yes	None
FVC worsening	Missing or mRSS worsening or no mRSS worsening	Alive	Yes	None
No FVC worsening	No mRSS worsening	Alive	No	None

FVC worsening means absolute decline since baseline in FVC percent predicted >10%

mRSS worsening means relative change from baseline in mRSS of >25% and absolute change from baseline of >5 points. In case baseline mRSS is 0 (and relative change can therefore not be calculated), then it will only be checked if the absolute change from baseline in mRSS is >5 points.

6.6.2.2 Categorical endpoints

In the analysis of the binary endpoints, patients with missing data will be considered as non-responders (i.e. worst case analysis).

6.6.2.3 Time-to-event endpoints

In the analyses of the time-to-event endpoints, missing or incomplete data will be managed by standard survival analysis techniques (i.e. censoring).

6.6.3 Other endpoints

6.6.3.1 Concomitant therapies

In case of (partially) missing start and end dates of concomitant therapies, the dates will be imputed so that the extent of exposure to the concomitant therapy is maximal, i.e. the first

day (month) of the month (year) for incomplete start dates and the last day (month) of the month (year) for incomplete end dates.

6.6.3.2 Safety endpoints

Missing or incomplete AE dates will be imputed according to BI standards (see “Handling of missing and incomplete AE dates”) (8).

6.6.3.3 Trial diagnosis date / Date of onset of Raynaud / Date of onset of first non-Raynaud symptom

In case of partially missing date of trial diagnosis or date of onset of Raynaud or date of onset of first non-Raynaud symptom, the following imputation will be done:

- If day is missing, then imputed day will be the 1st of the month
- If day and month are missing, then imputed date will be the 1st of January of the (non-missing) year
- If year is missing, date will not be imputed

6.6.3.4 Pharmacokinetic endpoints

Handling of missing PK data will be performed according to the BI standard procedure "Noncompartmental Pharmacokinetic / Pharmacodynamic Analyses of Clinical Studies" (001-MCS-36-472_RD-01) (6).

6.7 BASELINE, TIME WINDOWS AND CALCULATED VISITS

As a general rule, the last assessment/measurement before the date of first trial drug intake (included) will be used as baseline (possibly last screening assessment if no further available value).

Endpoints which are censored at Week 52 will be cut on Day 373 which is calculated as: Date of first trial drug intake (i.e. Day 1) + 372 (=365+7 day window per the CTP flow chart). All references to Day 373 throughout this document refer to this date which is 372 days after the date of first trial drug intake.

Visit windowing will be performed as described in [Tables 6.7: 1](#), [6.7: 2](#) and [6.7: 3](#), in order to assign data to the relevant study visit based on the actual day of the assessment. Data will be analysed using the re-calculated visits in the statistical tables. However, in the listings, all

visits performed will be displayed (even if outside time-window), along with the re-calculated visit.

Table 6.7: 1 Time windowing rules for spirometry, physical exam, vital signs, HCRU, mRSS, Digital ulcer, menstruation calendar

Time window of actual day ^[1]			Allocated to		
Start day	End day (included)	Length of the time-window [days]	Visit number	Visit name	Planned day of the visit
Last assessment before the date of first trial drug intake	1	1	1 or 2 ^[2]	Baseline	1
2	22	21	3	2 weeks	15
23	36	14	4	4 weeks	29
37	64	28	5	6 weeks	43
65	127	63	6	12 weeks	85

Table 6.7: 1 Time windowing rules for spirometry, physical exam, vital signs, HCRU, mRSS, Digital ulcer, menstruation calendar (cont'd)

Time window of actual day ^[1]			Allocated to		
128	211	84	7	24 weeks	169
212	309	98	8	36 weeks	253
310	373	63	9	52 weeks	365
374	533	161	10	68 weeks	477
534	645	112	11	84 weeks	589
646	708	63	12	100 weeks	701
709	Last trial drug intake + 27 ^[3]	Variable	NA	Between 100 weeks and follow-up visit	NA
Last trial drug intake + 28	Last trial drug intake + 35 ^[3]	7	FU	Follow-up	NA

Note: mRSS and Digital ulcer not measured at visits 3, 4, 5 and follow-up

[1] First trial drug intake date is taken into account as a reference to calculate time windows

[2] Depending on the last assessment before first trial drug intake (included), refer to [Section 6.7](#) for baseline definition

[3] These two periods only exist if follow-up visit occurs after 709 days (included)

Table 6.7: 2 Time windowing rules for SGRQ, FACIT-dyspnoea, SHAQ, EQ-5D-5L, patient global VAS, DLCO, SpO2, antoantibody assessment, Physician global VAS

Time window of actual day ^[1]			Allocated to		
Start day	End day (included)	Length of the time-window [days]	Visit number	Visit name	Planned day of the visit
Last assessment before the date of first trial drug intake	1	1	1 or 2 ^[2]	Baseline	1
2	253	252	7	24 weeks	169
254	373	280	9	52 weeks	365
374	708	175	12	100 weeks	701
709	Last trial drug intake + 27 ^[3]	Variable	NA	Between 100 weeks and follow-up visit	NA
Last trial drug intake + 28	Last trial drug intake + 35 ^[3]	7	FU	Follow-up	NA

[1] First trial drug intake date is taken into account as a reference to calculate time windows

[2] Depending on the last assessment before first trial drug intake (included), refer to [Section 6.7](#) for baseline definition

[3] These two periods only exist if follow-up visit occurs after 709 days (included)

Table 6.7: 3 Time windowing rules for laboratory measurements (and pregnancy test)

Time window of actual day ^[1]			Allocated to		
Start day	End day (included)	Length of the time-window [days]	Visit number	Visit name	Planned day of the visit
Last assessment before the date of first trial drug intake	1	1	1 or 2 ^[2]	Baseline	1
2	22	21	3	2 weeks	15
23	36	14	4	4 weeks	29
37	64	28	5	6 weeks	43
65	106	42	6	12 weeks	85
107	148	42	6a	18 weeks	127
149	190	42	7	24 weeks	169
191	232	42	7a	30 weeks	211
233	281	49	8	36 weeks	253
282	337	56	8a	44 weeks	309
338	373	56	9	52 weeks	365
374	449	56	9a	60 weeks	421
450	505	56	10	68 weeks	477
506	561	56	10a	76 weeks	533

Table 6.7: 3 Time windowing rules for laboratory measurements (and pregnancy test) (cont'd)

Time window of actual day ^[1]			Allocated to		
Start day	End day (included)	Length of the time-window [days]	Visit number	Visit name	Planned day of the visit
562	617	56	11	84 weeks	589
618	673	56	11a	92 weeks	645
674	708	35	12	100 weeks	701
709	Last trial drug intake + 27 ^[3]	Variable	NA	Between 100 weeks and follow-up visit	NA
Last trial drug intake + 28	Last trial drug intake + 35 ^[3]	7	FU	Follow-up	NA

[1] First trial drug intake date is taken into account as a reference to calculate time windows

[2] Depending on the last assessment before first trial drug intake (included), refer to [Section 6.7](#) for baseline definition

[3] These two periods only exist if follow-up visit occurs after 709 days (included)

If after windowing of visits at baseline, two values fall within the same baseline interval, then the last value will be taken into account. If after windowing of post-baseline visits, two visits fall in the same interval, then the measurement closest to the planned visit will be taken into account. In case two measurements are equidistant from the planned visit, then the last one will be picked.

7. PLANNED ANALYSIS

For End-Of-Text (EoT) tables ([1,2,5](#)), the set of summary statistics is: N / Mean / SD / Min / Median / Max. In descriptive statistics tables, mean, SD and median will be rounded to one additional digit than the raw individual value.

In case some endpoints show some extreme data, median, quartiles and percentiles will be presented additionally.

Tabulations of frequencies for categorical data will include all possible categories and will display the number of observations in a category as well as the percentage (%) relative to the respective treatment group (unless otherwise specified, all patients in the respective patient set whether they have non-missing values or not). Percentages will be rounded to one decimal place. The category missing will be displayed only if there are actually missing values.

7.1 DEMOGRAPHIC AND OTHER BASELINE CHARACTERISTICS

Only descriptive statistics are planned for this section of the report.

7.2 CONCOMITANT DISEASES AND MEDICATION

Only descriptive statistics are planned for this section of the report.

7.2.1 Baseline conditions

A summary of baseline conditions will be provided by treatment group, System Organ Class (SOC) and Preferred Term (PT). SOC and PT will be sorted by descending frequency over both treatment arms.

7.2.2 Concomitant therapies

Concomitant therapies will be described over several study periods:

- Previous therapies will be defined as treatments with an end date before first trial drug intake.
- Baseline therapies will be defined as treatments with a start date before first trial drug intake and a stop date after or on the day of the first trial drug intake (or ongoing after first trial drug intake).
- On-treatment concomitant therapies are defined as treatments with a start date after or on the day of first trial drug intake and before or on the day of last trial drug intake.
- Post-study drug discontinuation therapies are defined as treatments with a start date after last trial drug intake and before trial completion. This aims at flagging

concomitant treatments taken by patients having prematurely discontinued study medication but followed-up up to the end of the study.

Concomitant therapies will be described over the first 52 weeks, as well as over the entire duration of the study. Concomitant therapies over 52 weeks will be defined as follows:

- On-treatment concomitant therapies over 52 weeks are defined as treatments with a start date after or on the day of first trial drug intake and before or on either:
 - the day of last trial drug intake for patients having prematurely discontinued study medication before 52 weeks
 - the Week 52 time-point (Day 373 as defined in [Section 6.7](#)) for other patients.
- Post-study drug discontinuation concomitant therapies over 52 weeks are defined as treatments with a start date after last trial drug intake (for patients having prematurely discontinued study medication before 52 weeks) and before Week 52 time-point (Day 373 as defined in Section 6.7).

Table 7.2.2:1 summarises the concomitant therapy outputs which will be provided for each category of concomitant therapy created.

Summaries by ATC and preferred name (PN) will use the ATC3 code, and will be sorted by alphabetical ATC class and decreasing frequency of PN in the Nintedanib treatment arm within ATC class.

Summaries by Customised Drug Grouping (CDG) will be sorted alphabetically by the name of the CDG and by decreasing frequency of PN in the Nintedanib treatment arm within a CDG. CDGs are built using WHO-DD Standardised Drug Groupings (SDG), Sub-SDGs and ATC4 levels. CDGs are listed in [Section 9.4](#).

Table 7.2.2:1 Concomitant therapy outputs and position in the CTR

	By ATC and PN		By CDG and PN	
	Over 52 weeks	Entire trial duration	Over 52 weeks	Entire trial duration
Previous therapies	16.1.13.1	Not applicable	Not required	Not applicable
Baseline therapies	16.1.13.1	Not applicable	15.1	Not applicable
On-treatment concomitant therapies	16.1.13.1	16.1.13.1	16.1.13.1	16.1.13.1

Table 7.2.2:1 Concomitant therapy outputs and position in the CT (cont'd)

	By ATC and PN		By CDG and PN	
	Over 52 weeks	Entire trial duration	Over 52 weeks	Entire trial duration
All on-treatment concomitant therapies* with a frequency >2% in at least one treatment arm	16.1.13.1	Not required	Not required	Not required
All on-treatment concomitant therapies*	16.1.13.1	16.1.13.1	16.1.13.1	16.1.13.1
All concomitant therapies**	16.1.13.1	16.1.13.1	15.1	16.1.13.1
All concomitant therapies** in patients who prem. disc. treatment	Not required	Not required	16.1.13.1	Not required
Post-study drug discontinuation therapies	Not required	Not required	16.1.13.1	Not required

* including baseline therapies.

** including baseline, on-treatment and post-study drug discontinuation therapies.

7.3 TREATMENT COMPLIANCE

Only descriptive statistics are planned for this section of the report.

7.4 PRIMARY ENDPOINT(S)

All analyses will be performed on the Treated Set.

Refer to Section 7.3.1 of the CTP.

7.4.1 Primary analysis

The primary analysis will be performed on the TS (according to randomised treatment), using all available data from baseline (excluded) up to Week 52 (after time-windowing), including visits done after premature treatment withdrawal, EOT visits and follow-up visits done before Week 52. Patients will be analysed according to the ATA status stratum to which they belong to (as reported in the CRF), regardless of any mis-assignment to treatment based on identification of the wrong stratum in IXRS.

The primary analysis is a restricted maximum likelihood (REML) based approach using a random slope and intercept model.

The analysis will include the fixed, categorical effects of treatment, ATA status and gender, fixed continuous effects of time and baseline FVC (mL), age and height as well as the treatment-by-time and baseline-by-time interactions. Random effects will be included for patient response for both time and intercept.

The statistical model can be written as follows:

$$y_{ijkmg} = (\alpha + a_i + \phi_m + \vartheta_g + \vartheta_a Age_i + \vartheta_h Height_i + \beta_0 S_i + \tau_k) + (\gamma + g_i + \beta_s S_i + \varphi_k) t_{ij} + e_{ij}$$

$$(a_i, g_i) \sim N_2(\mathbf{0}, \Sigma)$$

$$e_{ij} \stackrel{iid}{\sim} N(0, \sigma^2)$$

The components of the model are as follows:

y_{ijkmg} = FVC value (mL) for patient i in ATA status stratum m with gender g at Week j receiving treatment k ,

α = mean patient intercept

a_i = random intercept effect for patient i , $i=1,2,\dots$

ϕ_m = the effect of ATA status stratum m , $m=1,2$. ATA status is used as reported in the CRF (“Positive” as the class of reference, regardless of any mis-assignment to treatment based on identification of the wrong stratum in IXRS)

ϑ_g = intercept coefficient of Gender covariate (“Male” as the class of reference)

ϑ_a = intercept coefficient of Age covariate

Age_i = Age covariate value [years] for patient i

ϑ_h = intercept coefficient of Height covariate

$Height_i$ = Height covariate value [cm] for patient i

β_0 = intercept coefficient of baseline effect

S_i = FVC baseline measurement [mL] of patient i

τ_k = intercept coefficient of the effect of treatment k , $k=1,2$

γ = mean patient slope

g_i = random slope effect for patient i

β_s = slope coefficient of baseline effect

φ_k = slope coefficient of the effect of treatment k

t_{ij} = time of measurement j for patient i , $j= 1,2,\dots J$

e_{ij} = the random error associated with the j^{th} Week of patient i . Measurement errors are independent and normally distributed with mean 0 and variance σ^2 , and uncorrelated with a_i and g_i .

Σ = a 2x2 unstructured covariance matrix

Within patient errors are assumed to follow a random coefficient regression model with random effect for intercept and slope. An unstructured variance-covariance structure will be

used to model these random slope and intercept. The variance-covariance matrix modeled to estimate the inter-individual variability is considered to have a Variance-Components structure. In the event of non-convergence, the following methods will be attempted (in order) to overcome it:

1. Add the 'singular=1e-10' option in the model statement – This raises the threshold at which columns are declared linearly dependent (from typically 1e-12).
2. Set 'maxiter=100' in the Proc Mixed statement – This increases the number of convergence iterations used from a default of 50.
3. Set 'scoring=4' to specify use of the Fisher scoring algorithm in the first 4 iterations.
4. Include the statement 'performance nothread' – this removes multi-threading from the calculations.

The first model to converge will be used as the primary analysis on the FVC rate of decline at week 52. If convergence does not achieved based on above approach, more simplified model can be used.

The Kenward-Roger approximation will be used to estimate denominator degrees of freedom and adjust standard errors. Significance tests will be based on least-squares means using a two-sided $\alpha = 0.05$ (two-sided 95% confidence intervals). The primary treatment comparison of slopes will be assessed through the treatment-by-time interaction coefficient.

Please refer to [Section 9.2](#) for more details concerning the statistical model and SAS code specifications.

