3.2 DISCUSSION OF TRIAL DESIGN, INCLUDING THE CHOICE OF CONTROL GROUP(S)

Patients with SSc-ILD will be included in this trial.

Placebo-controlled randomised trials provide the most robust results and are thus considered the most appropriate design, especially in rare patient populations, where multiple trials are not possible due to lack of patients.

Based on the efficacy and safety data collected in the development program of nintedanib in IPF, an adequately powered placebo-controlled Phase III trial of nintedanib (with the dose strength recommended for the treatment of IPF) will allow for sufficient efficacy and safety assessment in the SSc-ILD patient population, which has similarities to IPF in the underlying pathophysiology.

In situations where effective therapies are available, a placebo-controlled trial could be considered not to be ethical. Importantly, there is currently no approved pharmacotherapy to prevent progression of the ILD component of SSc, which is one of the main causes of death in patients with Systemic Sclerosis. To address the organ-specific manifestations, immunosuppressive agents (e.g. mycophenolate, cyclophosphamide, methotrexate, prednisone) are commonly used although randomised-controlled data for these therapies are scarce.

Preferably patients should not have a chronic immunosuppressive therapy when entering the trial. As chronic immunosuppressive therapy reflects the current clinical practice for treatment of progressive SSc-ILD, patients on background stable dose of mycophenolate mofetil / sodium or methotrexate are allowed in this trial.

Rescue treatment is allowed in case of clinically relevant deterioration of SSc, defined as either a FVC decrease $\geq 10\%$ compared to baseline or a mRSS score increase by >25% and >5 points or a relevant deterioration at any other organ system, see Section 4.2.2. By implementing these measures, the inclusion of a placebo arm is considered to be justified.

Proprietary confidential information © 2018 Boehringer Ingelheim International GmbH or one or more of its affiliated companies

As a positive ATA status is associated with progression of ILD (R14-5409), the randomization of patients will be stratified to two patients groups (ATA negative or ATA positive).

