7.3.1 Primary endpoint analyses

The primary endpoint is the annual rate of decline in FVC in mL estimated from measurements taken over 52 weeks. ATA status (positive or negative), age, height, gender and baseline FVC in mL will be included as explanatory variables in the model. Baseline FVC is defined as the FVC result recorded at Visit 2, unless missing in which case the screening result will be used. The decrease in FVC is assumed to be linear within each subject over the 52 weeks; this was also assumed in the idiopathic pulmonary fibrosis trials INPULSIS-1 and INPULSIS-2 (P14-07514). The intercepts and slopes will be assumed to be normally distributed with arbitrary covariance matrix. The within patient error will be assumed to be independent and normally distributed with mean zero and a common variance. The Kenward-Roger approximation will be used to estimate denominator degrees of freedom. Significance tests will be based on least-squares means using a two-sided $\alpha = 0.05$, and an intent-to-treat principle will be used (i.e. all available data up to 52 weeks will be used, including baseline and data for patients who prematurely discontinue randomised treatment). Analyses will be implemented using SAS® version 9.4 or higher.

The assumptions for the primary analysis of decline in FVC will be tested as described in the trial statistical analysis plan (TSAP). The primary analysis will be based on observed data and will assume data are missing at random. The effect of missing data will be investigated using multiple imputation methods which assume that patients who discontinue treatment will no longer benefit from it in the future. See Section 7.5.1 for further details of these sensitivity analyses.

Page 80 of 126

Proprietary confidential information © 2018 Boehringer Ingelheim International GmbH or one or more of its affiliated companies

Subgroup analyses (for example, by gender, age, ATA status, SSc subtype and subgroups reflecting disease severity) will be specified in the TSAP.

A cumulative distribution plot will be provided, showing the percentage of patients by the change from baseline in FVC in mL at week 52.

FVC data collected beyond week 52 will be analysed in a descriptive manner only. Data will be summarised graphically and using summary statistics.

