7.6 RANDOMISATION

Patients will be randomised in blocks to double-blind treatment. The randomization will be stratified by ATA status (positive or negative) within the IRT system. Approximately equal numbers of patients will be randomised to each treatment group (i.e. a 1:1 randomisation will be used). BI will arrange for the randomization and the packaging and labelling of trial medication. The randomisation list will be generated using a validated system, which involves a pseudo-random number generator so that the resulting treatment will be both reproducible and non-predictable. The block size will be documented in the clinical trial report. Access to the codes will be controlled and documented. All members of the clinical trial team will remain blinded to the randomization schedule until the final database is locked. The independent DMC will at any time have the possibility to look at unblinded data according to the DMC charter.

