7.7 DETERMINATION OF SAMPLE SIZE

The estimated treatment difference in the absolute change in FVC in mL over 52 weeks is assumed to be between 70 and 110 mL, based on the cyclophosphamide trial in scleroderma lung disease (R14-5407), and on the idiopathic pulmonary fibrosis (IPF) trials INPULSIS-1 and INPULSIS-2 (P14-07514). Note that FVC percent predicted has been converted to mL using the approximate relationship of 1% = 35 mL based on the IPF results which were

Trial Protocol

Page 85 of 126

Proprietary confidential information © 2018 Boehringer Ingelheim International GmbH or one or more of its affiliated companies

presented in both percent predicted and mL. An equal standard deviation across treatment groups of 245 mL (based on the cyclophosphamide trial) and a 1:1 randomization is assumed. The sample size calculations in Table 7.7:1 have been performed based on a two-sided, two-sample superiority t-test, with a significance level of 5% and power of either 80% or 90%.

Table 7.7: 1 Primary endpoint: Sample size calculations based on a two-sided, two-sample t-test with a significance level of 5% and various assumptions

Mean treatment difference in absolute change in FVC in mL	50	50	70	70	110	110
Standard deviation of FVC in mL	245	245	245	245	245	245
Power (%)	90	80	90	80	90	80
Sample size per treatment group	506	378	259	194	106	79

The first key secondary endpoint of the absolute change from baseline in the mRSS at week 52 is also considered. Based on skin thickness results from the cyclophosphamide trial in scleroderma lung disease (R14-5407), the estimated treatment difference is assumed to be between 2 and 3 points. An equal standard deviation across treatment groups of 9 (based on the same reference) and a 1:1 randomization is assumed. The sample size calculations in Table 7.7: 2 have been performed based on a two-sided, two-sample superiority t-test, with a significance level of 5% and power of either 80% or 90%.

Table 7.7: 2 First key secondary endpoint: Sample size calculations based on a two-sided, two-sample t-test with a significance level of 5% and various assumptions

Mean treatment difference in absolute change in mRSS	3	3	2	2	2.2	2.6
Standard deviation of mRSS	9	9	9	9	9	9
Power (%)	90	80	90	80	80	90
Sample size per treatment group	191	143	427	319	260	260

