9.2 COMPLEMENTARY INFORMATION ON STATISTICAL MODEL AND SAS CODE

Primary endpoint model (and other rate of decline endpoints):

The key code is given below. Time is defined as duration since first trial drug intake divided by 365.25. Visit is the visit number.

Meanbase corresponds to the overall mean baseline for the endpoint.

```
proc MIXED data=FVC cl method=reml order= formatted covtest;
  CLASS patient visit treatment gender ata;
  MODEL endpoint= gender age height ata fvcbaseline fvcbaseline*time
  treatment treatment*time /solution CL ddfm=KR;
  RANDOM intercept time/ type=un subject=patient;

  ESTIMATE 'Nintedanib' fvcbaseline*time MEANBASE treatment*time 0 1 /
e CL;
  ESTIMATE 'Placebo' fvcbaseline*time MEANBASE treatment*time 1 0 / e
CL;
  ESTIMATE 'Nintedanib 150mg bid - Placebo' treatment*time -1 1 / e CL;
RUN;
```

Primary endpoint subgroup analysis model:

This is the case of subgroups with 2 categories:

```
proc MIXED data=FVC cl method=reml order= formatted covtest;
  CLASS patient visit treatment gender ata subgroup;
  MODEL endpoint= gender age height ata fvcbaseline fvcbaseline*time
  treatment*subgroup treatment*subgroup*time /solution CL ddfm=KR;
  RANDOM intercept time/ type=un subject=patient;

  ESTIMATE 'Nintedanib - Subgroup A' fvcbaseline*time MEANBASE treatment *
subgroup *time 0 0 1 0 / cl e;
  ESTIMATE 'Placebo - Subgroup A' fvcbaseline*time MEANBASE treatment *
subgroup *time 1 0 0 0 / cl e;

  ESTIMATE 'Nintedanib - Subgroup B' fvcbaseline*time MEANBASE treatment *
subgroup *time 0 0 0 1 / cl e;
  ESTIMATE 'Placebo - Subgroup B' fvcbaseline*time MEANBASE treatment *
subgroup *time 0 1 0 0 / cl e;

  ESTIMATE 'Nintedanib - Placebo Subgroup A' subgroup * treatment *time -1
0 1 0 / e CL;
```

```
'Week 52, Subgroup 3'  
0 0 0 0 0 0 0 0  
0 0 0 0 0 0 0 0  
0 0 0 0 0 0 0 0  
0 0 0 0 0 0 0 0  
0 0 0 0 0 0 0 0  
0 0 0 0 0 0 0 0  
0 0 0 0 0 0 0 0  
1 1 -3 1 -1 -1 3 -1,
```

```
'Week 52, Subgroup 4'  
0 0 0 0 0 0 0 0  
0 0 0 0 0 0 0 0  
0 0 0 0 0 0 0 0  
0 0 0 0 0 0 0 0  
0 0 0 0 0 0 0 0  
0 0 0 0 0 0 0 0  
0 0 0 0 0 0 0 0  
1 1 1 -3 -1 -1 -1 3
```

```
/divisor=4 joint elsm cl alpha=0.05;  
RUN;
```

For 2 subgroups, the LSMESTIMATE will write:

```
LSMESTIMATE visit*treatment*subgroup
```

```
'Week 52, Subgroup 1'  
0 0 0 0  
0 0 0 0  
0 0 0 0  
0 0 0 0  
0 0 0 0  
0 0 0 0  
-1 1 1 -1,
```

```
'Week 52, Subgroup 2'  
0 0 0 0  
0 0 0 0  
0 0 0 0  
0 0 0 0  
0 0 0 0  
0 0 0 0  
1 -1 -1 1
```

```

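### The primary slope model adjusts for ATA, the only stratification factor, in the intercept but not in the slope, so the treatment-by-time test is slightly conservative

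*SAP*

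**What the plan says.** Protocol 7.6 names one stratification factor: "The randomization will be stratified by ATA status (positive or negative) within the IRT system". Protocol 3.2 gives the reason: "As a positive ATA status is associated with progression of ILD".

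Protocol 7.3.1 puts ATA in the primary model without saying whether it acts on level or slope: "ATA status (positive or negative), age, height, gender and baseline FVC in mL will be included as explanatory variables in the model".

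SAP 7.4.1 is specific. Its text states "The analysis will include the fixed, categorical effects of treatment, ATA status and gender", and the only interactions come later in the same sentence: "as well as the treatment-by-time and baseline-by-time interactions". In the equation the ATA term stands in the intercept bracket. The slope bracket holds the mean slope, the patient's random slope, baseline FVC and treatment. The code in SAP 9.2 agrees: "MODEL endpoint= gender age height ata fvcbaseline fvcbaseline*time", followed by the treatment terms and no `ata*time`.

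The hypothesis test is on the slope: "The primary treatment comparison of slopes will be assessed through the treatment-by-time interaction coefficient".

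The two covariate sensitivity models in SAP 7.4.2.2.2 keep the same two interactions. ATA-specific slopes appear only in the ATA subgroup analysis (SAP 6.4, 7.4.3), through treatment-by-subgroup-by-time.

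**The concern.** The factor was stratified on because it is expected to predict how fast the lung disease progresses, and the endpoint is a rate of progression. An intercept term adjusts the FVC level. It reaches the slope only indirectly, through the intercept-slope covariance, and that is not adjustment of the slope.

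Stratified randomisation balances ATA between arms, so the true sampling variance of the treatment-slope difference excludes the between-stratum slope variance. A model without ATA-by-time does not know this and counts that variance as random-slope variance. The reported standard error is then larger than it should be. At stake are a little power and the match between how patients were randomised and how the slope is analysed.

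**Working it through.** **1. The plan's own figure.** Inputs from Protocol 7.7: difference 70 mL, SD 245 mL, two-sided 5%, 90% power, 1:1 allocation. The normal approximation gives n = 2(1.960 + 1.282)² × 245² / 70² = 257.4, so 258. The exact noncentral-t calculation gives 259, as in Table 7.7: 1, and the other five cells of that table also match. At the planned 260 per arm, power is 90.2%.

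**2. Variance left in the slope.** With ATA-positive share p and ATA slope difference d (mL/yr), omitting ATA-by-time leaves p(1−p)d² in the random-slope variance. Neither p nor d is in the documents. With p = 0.6 (assumed), p(1−p) = 0.24:
- d = 50: 600
- d = 100: 2,400
- d = 150: 5,400

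**3. Effect on the standard error.** Assume a within-stratum slope SD of 200 mL/yr, an error SD of 100 mL, complete data and the spirometry visits at weeks 2, 4, 6, 12, 24, 36 and 52 (Protocol flowchart). In years, the sum of squared deviations of these times is Sxx = 0.784, so 100²/Sxx = 12,760. Then

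SE² = (2/260) × (200² + 100²/Sxx + extra),

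where extra = p(1−p)d² without the term and 0 with it.

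| d (mL/yr) | SE without `ata*time` | SE with | Overstatement |
|---|---|---|---|
| 50 | 20.26 | 20.15 | 0.6% |
| 100 | 20.60 | 20.15 | 2.2% |
| 150 | 21.15 | 20.15 | 5.0% |

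**4. Effect on power and alpha, on the protocol's scale.** Hold the total SD at 245 mL, so the SD after adjustment is s = √(245² − 0.24d²). The actual two-sided alpha of the unadjusted test is 2[1 − Φ(1.96 × 245/s)].

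| d (mL/yr) | s (mL) | Power at 260 per arm | n per arm for 90% | Alpha without the term |
|---|---|---|---|---|
| 0 | 245.0 | 90.2% | 259 | 0.050 |
| 50 | 243.8 | 90.5% | 256 | 0.049 |
| 100 | 240.1 | 91.3% | 249 | 0.045 |
| 150 | 233.7 | 92.6% | 236 | 0.040 |

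Letting p run from 0.4 to 0.7 gives power of 90.4–90.5%, 91.2–91.3% and 92.3–92.7% for the three non-zero values of d.

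**5. Simulation check.** REML random intercept-and-slope model, 260 per arm, 400 replicates, p = 0.6, balanced ATA, total SD 245, error SD 100 and intercept SD 80 (the last two assumed). For d = 100 and a true effect of 70, the mean estimate is 69.5 with or without the term, the mean SE is 20.2 without and 19.7 with it, and power is 95.0% and 95.8%. Under no effect both models reject in 4.8% of replicates. The Monte Carlo error there is √(0.05 × 0.95/400) = 1.1 points, too coarse to show the small conservatism in step 4. Simulated power exceeds 90% because the slope model uses all visits, as Protocol 7.7 anticipates.

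**6. If balance is lost.** A 5-point ATA imbalance shifts the unadjusted slope difference by about 0.05d, or 5 mL/yr at d = 100. In simulation with no true effect the mean estimate was −5.1 mL/yr without the term and −0.4 with it.

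**The case against.** The strongest reply is that nothing is invalid. With ATA balanced, the estimate is the same under both models and type I error is not inflated. Nor is power lost against the plan: the trial was sized by a "two-sample superiority t-test, with a significance level of 5"% on an overall SD of 245 mL, with no reduction for ATA, so the planned 90% already carries any between-stratum variance. All of that stands.

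It is also true that the size rests on assumptions. A difference of 150 mL/yr is about twice the 70 mL used for sizing and above the 110 mL upper end of the assumed treatment effect, so it should not be the headline.

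Nor is the change free. With `ata*time` as a class interaction, the per-arm ESTIMATE statements in SAP 9.2 become non-estimable as written; only the treatment difference is unaffected. The imputation steps draw on per-arm slopes, and for sensitivity analyses 1 and 2 these come from a fit to pattern 2 alone, which SAP 7.4.2.1.2 permits with as few as 11 patients. These points limit the fix but do not remove the case for it.

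The ATA subgroup model does not fill the gap, because it is not the confirmatory test.

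A reader might infer that the primary comparison is biased, or that the SAP contradicts the protocol. The documents support neither. Randomisation is stratified by ATA, and Protocol 7.3.1 asks only for ATA as an explanatory variable, which the SAP provides.

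**Conclusion.** The point holds as a matter of precision and calibration, not validity. Text, equation and code agree that ATA does not act on the slope, and no covariate sensitivity model adds it. The test is slightly conservative: for an ATA slope difference of 50 to 100 mL/yr the standard error is 0.6% to 2.2% too large, and about 0.3 to 1.1 points of power are forgone. At 150 mL/yr the figures are 5.0% and about 2.4 points (92.6 − 90.2). All of these rest on an assumed 60% ATA-positive share and assumed slope differences. The standard-error figures also assume slope SD 200 and error SD 100; the power figures assume a total SD of 245 mL.

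The absence of bias depends on balance. SAP 7.4.1 uses ATA as recorded in the CRF whatever stratum was entered at randomisation, and SAP 6.2 lists a wrong stratification factor as an important protocol violation (C2), so some loss of balance is foreseen. The documents give no reason to expect it to be large.

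**What to change.** Before unblinding:
- Add `ata*time` to the MODEL statement of the primary FVC analysis (SAP 7.4.1, 9.2), the FVC % predicted slope analysis (7.5.2.1), the on-treatment sensitivity analysis (7.4.2.1.1) and both covariate sensitivity models (7.4.2.2.2). Add the matching ATA slope term to the equation.
- Add prespecified ATA weights on `ata*time` to the per-arm ESTIMATE statements, for example the observed overall proportions. Leave the treatment-difference ESTIMATE as it is.
- State in SAP 7.4.2.1.2 and 9.2 that the imputation-step model fitted to pattern 2 alone need not carry the term, because numbers there may be very small.

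The cost is one degree of freedom among about 520 patients and a small edit to the per-arm estimates. Protocol 7.3.1 is compatible with the change as worded.
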